### **11.5 Interim Analysis**

Given the size of the trial and since the study agent is a local anesthetic that is given only once, and has been used in similar situations before, we will not conduct an interim analysis. We will not have any stopping rules based upon our study endpoint. This is reasonable given that both control and intervention arm subjects

will be given the standard of care (i.e. all will receive at least 20mL of 0.25% bupivacaine).

However, at 50% accrual rate we will review procedure and resolve study-specific problems that may arise (e.g. problems with REDCap, issues with the survey instrument, etc.). Any changes that are deemed necessary at this point will be resubmitted to the IRB as an addendum.

## 11.6 Reporting and Exclusions

**11.6.1 Evaluation of toxicity.** All patients will be evaluable for toxicity from the time of their first treatment with liposomal bupivacaine.

**11.6.2 Evaluation of response.** All patients included in the study will be assessed for response to treatment if they have received at least 1 treatments.

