### 12.2 Definition of SAE

SAE's include death, life threatening adverse experiences, hospitalization or prolongation of hospitalization, disability or incapacitation, overdose, congenital anomalies and any other serious events that may jeopardize the subject or require medical or surgical intervention to prevent one of the outcomes listed in this definition.

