#### 12.2.1 Reporting of SAE to IRB

All SAEs occurring on this study will be reported to the IRB according to the IRB policy, which can be accessed via the following link:  
[http://researchintegrity.weill.cornell.edu/forms\\_and\\_policies/forms/Immediate Reporting Policy.pdf](http://researchintegrity.weill.cornell.edu/forms_and_policies/forms/Immediate%20Reporting%20Policy.pdf).

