### 13. Data and Safety Monitoring Plan (DSMP)

In this section, please include a written plan of the measures that will be taken to ensure the safety of clinical research subjects and protect the validity and integrity of research data. The following questions should be addressed as a part of the DSMP and must be incorporated into your WCM eIRB application:

- Adverse events will be recorded by the study nurse and clinical fellow during follow-up phone calls and clinic visits with each post-operative patient. Minor adverse events will be examined and reviewed for intervals of every 10 patients during accrual. Any significant adverse events (allergic reaction, central nervous system or cardiotoxicity) will trigger a temporary cessation of the trial and full review by the principal investigator.
  - Study stopping rules/protocol: the only stopping rule is if an SAE occurs, the study will be stopped fully. A full review by the PI will then take place and the IRB, FDA, and Pacira Pharmaceuticals, Inc. will be queried as to when and if the study should continue.
- Data
  - Adverse event data
    - Major: Allergic reaction, central nervous system and cardiotoxicity
    - Minor: poor pain control, extended hospital stay, wound infection, scrotal hematoma, wound dehiscence, urinary retention, nausea, vomiting, diarrhea
  - Study-related data
    - Pain scores (NRS-11), Narcotic tablet tally, overall pain control satisfaction (Yes/No question)
  - Demographics
  - Patient age, male infertility diagnoses (i.e. presence of varicocele), prior surgical history, current medications, historical lab evaluation (FSH, LH, total testosterone, semen analyses, sperm DNA integrity tests such as tunel or SCSA assay, karyotype data, y-microdeletion status), pathology results of testis biopsy
- Data safety
  - Data will be kept in REDCap, which is licensed by WCMC and is HIPAA compliant. Only study personnel will have access to the database. Hard or software copies of the database will not be allowed. The database will only be accessed within the WCMC network utilizing WCMC tagged devices. Patient identifiers will be replaced by study identifiers as soon as data collection is complete.

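### Section 13 lists an extended hospital stay as a minor event although 12.2 makes prolonged hospitalization an SAE; secondarily, 11.6.1 starts toxicity evaluability at a drug the controls never receive

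*Combined protocol and SAP*

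**What the plan says.** **Routing of adverse events.** Section 13 sets out three routes.
- Minor events: "Minor adverse events will be examined and reviewed for intervals of every 10 patients during accrual".
- Significant events: "Any significant adverse events (allergic reaction, central nervous system or cardiotoxicity) will trigger a temporary cessation of the trial", with a full review by the principal investigator.
- SAEs: "the only stopping rule is if an SAE occurs, the study will be stopped fully", after which the IRB, the FDA and the manufacturer are consulted on whether to resume.

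Under its data heading, Section 13 then gives two lists. One is "Major: Allergic reaction, central nervous system and cardiotoxicity". The other begins "Minor: poor pain control, extended hospital stay, wound infection" and goes on to hematoma, dehiscence, urinary retention and gastrointestinal symptoms.

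**SAE rules.** Section 12.2 includes "hospitalization or prolongation of hospitalization" among its criteria. Section 12.2.1 says "All SAEs occurring on this study will be reported to the IRB according to the IRB policy". Section 12.2.2 requires FDA notice no later than 7 calendar days after the information is first received, and 12.2.3 sends copies to the manufacturer. Separately, 12.1.4 puts all adverse events, serious or not, under the IRB's reporting policy.

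**Toxicity population.** Section 11.6.1 says "All patients will be evaluable for toxicity from the time of their first treatment with liposomal bupivacaine". Under 5.2 the control arm receives 40 mL of 0.25% standard bupivacaine and no liposomal product. Section 11.1 plans 25 patients per arm.

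**The concern.** An extended hospital stay and a prolonged hospitalization are, in ordinary reading, the same thing. Section 13 calls it minor and 12.2 calls it serious, and the consequences differ greatly: periodic review on one side, a full stop and expedited notice on the other. The study nurse and clinical fellow record events under Section 13, so its label is the one they are likely to have in front of them. At stake is whether an unplanned admission after surgery is classified correctly at the outset.

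The sentence in 11.6.1 raises a smaller matter. It is the only rule in the statistical section that says who counts for toxicity, and it ties the start to the investigational drug. A safety table built on it literally would have no control column. Section 2.4 rests the risk/benefit case partly on similar reaction rates for the two preparations, and a one-arm table could not speak to that.

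**Working it through.** The point is textual, so the check sets the rules side by side.

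**1. Does the minor list feed the ten-patient review?** Section 13 does not say so outright. But its major list names the same three conditions (allergic reaction, central nervous system toxicity, cardiotoxicity) as the sentence on significant events that pause the trial. If major corresponds to significant, the other list corresponds to the minor events sent to batch review. This is an inference, but the natural one.

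**2. Where does one event go?** Take a patient kept in hospital longer than planned.

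| Rule | Classification | Consequence |
|---|---|---|
| Section 13, minor list | Minor | Reviewed at the next ten-patient interval |
| 12.2 | SAE | Full stop (Section 13); IRB report (12.2.1); FDA notice within 7 calendar days (12.2.2); copy to the manufacturer (12.2.3) |

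Both rows apply to the same event, and no sentence ranks them explicitly.

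**3. Is this item different from the rest of the minor list?** Yes. Wound infection, hematoma or vomiting are conditions that may or may not lead to admission; each becomes an SAE only if it meets a 12.2 criterion. An extended hospital stay is not a condition but an outcome, and it is close to the very outcome 12.2 uses to define seriousness. It is therefore the one listed item whose name by itself points to the SAE route.

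**4. Who has a start point under 11.6.1?** Planned treated patients: 25 + 25 = 50 (11.1, 11.2). Patients who receive liposomal bupivacaine: 25. Patients with no literal start point: 50 − 25 = 25, that is 25/50 = 50%, the whole control arm.

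**5. Are control data lost?** No. Table 1 in 5.1 schedules adverse event evaluation on the day of procedure, in the first week and at the post-operative visit without restriction by arm. Section 10.1 captures toxicity and adverse event data for all enrolled patients. Section 13 records events for each post-operative patient. Adverse event records lost: 0.

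**6. Does either point touch the design?** No. The stated power is 85% for a 2.4-point difference, SD 2.75, 25 per arm, two-sided alpha 0.05 (11.1, 11.2). The standardized difference is 2.4/2.75 = 0.873, and the exact two-sample t calculation gives 85.6%, which reproduces the stated figure. None of these inputs depends on the safety wording.

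**The case against.** **The SAE rules already decide the matter.** Seriousness under 12.2 depends on outcome and applies to any event. Sections 12.2.1 and 12.2.2 allow no exception, and the full-stop rule stands in the same section as the minor list. Even a mislabelled event falls under the IRB policy through 12.1.4, though the timing in that policy is not in the documents. This stands, and it is why the effect is small. It does not remove the conflicting label.

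**The term may be innocent.** Surgery takes place at an ambulatory surgical center (Section 5, Visit two), so the item may mean only a longer same-day recovery. That is possible, but the term is undefined and no text draws the line.

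**11.6.1 is a slip.** Its subject is all patients, the collection rules cover both arms, and 11.4 plans no between-arm toxicity analysis, so no planned comparison is damaged. This also stands; the sentence needs correcting, not the design.

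**Stronger readings a reader might infer.** One could turn the ten-patient interval into calendar time at the planned accrual rate and conclude that SAE reports would miss the 7-day limit. The documents do not support this. It requires staff to disregard 12.2, 12.2.1, 12.2.2 and the stopping rule together. It also sets a periodic review interval against a clock that starts when the information is received. Likewise, one could infer that control-arm safety data will not exist; 5.1, 10.1 and Section 13 show that they will.

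**Conclusion.** Both conflicts are in the current text, and the first is the more important. Section 13 gives a minor label to an event that 12.2, on its plain wording, makes serious. The likely result is still correct handling, because the SAE rules probably prevail; the remaining risk is misclassification of an unplanned admission. How often that could arise cannot be stated, because the documents give no expected number of such stays. The conclusion assumes that the minor list is the set sent to ten-patient review and that an extended stay can include an admission.

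The second is a correction of wording. Read literally, 11.6.1 leaves 25 of 50 treated patients outside the toxicity set; the evident intent is both arms.

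Severity is minor. Adverse event capture, power and the primary analysis are unaffected.

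**What to change.** In Section 13, remove the extended-stay item from the minor list, or limit it to *longer same-day recovery without admission*. Add: *Any event meeting 12.2 follows the SAE route whatever the minor list says.* That sentence also covers the other listed conditions when they lead to admission.

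In 11.6.1, replace the start point with *from the time of study local anesthetic administration in either arm*, so that safety can be summarised by arm. A descriptive table without a test is enough.

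The cost is two wording changes in one amendment and one table from data already being collected. The small downside is that an unplanned admission then clearly triggers the full stop, but 12.2 and the stopping rule in Section 13 already require that.

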## 12. Adverse Event Reporting Requirements

Adverse event (AE) monitoring and reporting is a routine part of every clinical trial. The investigator will be required to provide appropriate information concerning any findings that suggest significant hazards, contraindications, side effects, or precautions pertinent to the safe use of the drug or device under investigation. Safety will be monitored by evaluation of adverse events reported by patients or observed by investigators or research staff, as well as by other investigations such as clinical laboratory tests, x-rays, electrocardiographs, etc.

### 12.1 Adverse Event Definition

An adverse event (also referred to as an adverse experience) can be any unfavorable and unintended sign (e.g., an abnormal laboratory finding), symptom, or disease temporally associated with the use of a drug, and does not imply any judgment about causality. An adverse event can arise with any use of the drug (e.g., off-label use, use in combination with another drug) and with any route of administration, formulation, or dose, including an overdose.

#### 12.1.1 Investigational Agent or Device Risks

Liposomal bupivacaine carries the same risks of CNS toxicity (either excitation or depression) and cardiovascular toxicity (nodal blockade, arrhythmia) as standard bupivacaine. These toxicity events occur in approximately 1 out of every 50,000 patients (please refer to the attached FDA Report, page 79). There is also a risk of allergic reaction. The likelihood of these events are exceedingly small, but warrant monitoring nevertheless. More pertinently, major drug interactions

occur with simultaneous administration with lidocaine, which may destabilize the liposomes and cause premature release of the agent. We do not plan on using any lidocaine due to this reason. Both standard and liposomal bupivacaine are metabolized in the liver and excreted primarily by the kidneys. We plan to exclude men with either hepatic or renal impairment.

#### 12.1.2 Adverse Event Characteristics and Related Attributions

**CTCAE term (AE description) and grade:** The descriptions and grading scales found in the revised NCI Common Terminology Criteria for Adverse Events (CTCAE) version 4.0 will be utilized for AE reporting. A copy of the CTCAE version 4.0 can be downloaded from the CTEP web site (<http://ctep.cancer.gov>).

- **Attribution** of the AE:
  - Definite – The AE *is clearly related* to the study treatment.
  - Probable – The AE *is likely related* to the study treatment.
  - Possible – The AE *may be related* to the study treatment.
  - Unlikely – The AE *is doubtfully related* to the study treatment.
  - Unrelated – The AE *is clearly NOT related* to the study treatment.

#### 12.1.3 Recording of Adverse Events

All adverse events will be recorded on a patient specific AE log in REDCap. The AE log will be maintained by the research staff on REDCap and appropriate documentation will also be kept in the patient's chart.

#### 12.1.4 Reporting of AE to WCM IRB

All AEs occurring on this study will be reported to the IRB according to the IRB policy, which can be accessed via the following link:  
[http://researchintegrity.weill.cornell.edu/forms\\_and\\_policies/forms/Immediate\\_Report\\_Policy.pdf](http://researchintegrity.weill.cornell.edu/forms_and_policies/forms/Immediate_Report_Policy.pdf).

### 12.2 Definition of SAE

SAE's include death, life threatening adverse experiences, hospitalization or prolongation of hospitalization, disability or incapacitation, overdose, congenital anomalies and any other serious events that may jeopardize the subject or require medical or surgical intervention to prevent one of the outcomes listed in this definition.

#### 12.2.1 Reporting of SAE to IRB

All SAEs occurring on this study will be reported to the IRB according to the IRB policy, which can be accessed via the following link:  
[http://researchintegrity.weill.cornell.edu/forms\\_and\\_policies/forms/Immediate Reporting Policy.pdf](http://researchintegrity.weill.cornell.edu/forms_and_policies/forms/Immediate%20Reporting%20Policy.pdf).

#### 12.2.2 Reporting of SAE to FDA

If an SAE occurs on this study, the event will be filed on a MedWatch form with the FDA. The investigator must notify the FDA of any SAE's as soon as possible but no later than 7 calendar days after the initial receipt of the information

#### 12.2.3 Reporting of SAE to Pacira Pharmaceuticals, Inc.

The institution will send Pacira Pharmaceuticals, Inc. copies of any and all serious adverse event reports filed with the FDA or other applicable regulatory authorities, as well as copies of any correspondence with the FDA or other applicable regulatory authorities, regarding any and all serious adverse events, irrespective of association with the Study Drug(s) in the course of the Clinical Trial, within five (5) business days of such report or correspondence being sent to the FDA or other applicable regulatory authorities. Copies will be faxed directly to Pacira Pharmaceuticals, Inc. Safety Department.

### **12.4 AE/SAE Follow Up**

Please specify any follow up procedures for any AEs/SAEs that occur on study. Sample language is provided below in *italics*.

All SAEs and AEs reported during this study will be followed until resolution or until the investigator confirms that the AE/SAE has stabilized and no more follow-up is required. This requirement indicates that follow-up may be required for some events after the patient discontinues participation from the study.

### 13. Data and Safety Monitoring Plan (DSMP)

In this section, please include a written plan of the measures that will be taken to ensure the safety of clinical research subjects and protect the validity and integrity of research data. The following questions should be addressed as a part of the DSMP and must be incorporated into your WCM eIRB application:

- Adverse events will be recorded by the study nurse and clinical fellow during follow-up phone calls and clinic visits with each post-operative patient. Minor adverse events will be examined and reviewed for intervals of every 10 patients during accrual. Any significant adverse events (allergic reaction, central nervous system or cardiotoxicity) will trigger a temporary cessation of the trial and full review by the principal investigator.
  - Study stopping rules/protocol: the only stopping rule is if an SAE occurs, the study will be stopped fully. A full review by the PI will then take place and the IRB, FDA, and Pacira Pharmaceuticals, Inc. will be queried as to when and if the study should continue.
- Data
  - Adverse event data
    - Major: Allergic reaction, central nervous system and cardiotoxicity
    - Minor: poor pain control, extended hospital stay, wound infection, scrotal hematoma, wound dehiscence, urinary retention, nausea, vomiting, diarrhea
  - Study-related data
    - Pain scores (NRS-11), Narcotic tablet tally, overall pain control satisfaction (Yes/No question)
  - Demographics
  - Patient age, male infertility diagnoses (i.e. presence of varicocele), prior surgical history, current medications, historical lab evaluation (FSH, LH, total testosterone, semen analyses, sperm DNA integrity tests such as tunel or SCSA assay, karyotype data, y-microdeletion status), pathology results of testis biopsy
- Data safety
  - Data will be kept in REDCap, which is licensed by WCMC and is HIPAA compliant. Only study personnel will have access to the database. Hard or software copies of the database will not be allowed. The database will only be accessed within the WCMC network utilizing WCMC tagged devices. Patient identifiers will be replaced by study identifiers as soon as data collection is complete.

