## 2.2 Investigational Agent or Device

Liposomal bupivacaine has garnered significant interest in the peri-operative arena. Multiple studies have now documented varying levels of success with intra-operative administration [1-3]. Relevant to our patient population, the liposomal delivery vehicle provides an extended release over 72 hours, which corresponds to the time-period of maximum narcotic utilization in men undergoing testicular sperm extraction. For this latter reason, we believe liposomal bupivacaine to be a promising adjunct to manage our patient population. As standard practice, we currently use 1/4% bupivacaine hydrochloride infiltrated into the peri-testicular tissue, the spermatic cord, and the scrotal wound. This agent only provides analgesia for ~6 hours.

The mechanism of action for both bupivacaine hydrochloride and liposomal bupivacaine is the same, intracellular binding of voltage gated sodium channels. This blockade prevents pain fibers from initiating and propagating an action potential. In the case of liposomal bupivacaine, the agent is packaged into liposomes in order to slow the release of the medication. This extends the theoretical period of action from 6 to ~72 hours. The Phase III trials that studied liposomal bupivacaine utilized a dose of 120mg [4] and 266mg [5]. These studies found liposomal bupivacaine effective against placebo for bunionectomy and hemorrhoidectomy [4-5]. Subsequently, a multitude of studies have used the 20mL vial (266mg), best described by a Cochrane Review/Meta-analysis [6]. These studies found a similar safety profile of liposomal bupivacaine compared to the standard preparation of bupivacaine. The pharmacokinetics were as follows:  $T_{1/2}$  23.8 – 34.1 hours,  $C_{max}$  166 – 867 ng/mL, and  $T_{max}$  0.5 – 2 hours [4-5,7]. Liposomal bupivacaine carries the same risks of CNS toxicity and cardiovascular toxicity as standard bupivacaine. Major drug interactions occur with simultaneous administration with lidocaine, which may destabilize the liposomes and cause premature release of the agent. We do not plan on use lidocaine due to this reason. Both standard and liposomal bupivacaine are metabolized in the liver and excreted primarily by the kidneys. We plan to exclude men with either hepatic or renal impairment.

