##### **Post-operative recovery: week 1**

Study participants will complete online surveys generated from RedCap x 7 days. The survey will be administered every 8 hours in days 1-2, and every 12 hours in days 3-7. The surveys will ask the patients to rank their current pain (NRS-11), pain control satisfaction, and record the number of narcotic tablets required.

During the standard of care post-op call, the nurse will ask and record complications and also address patient questions.

Post-op visit (2-3 weeks post-op):

The post-op clinic visit allows for a routine wound check and a discussion of results. The subject will have an opportunity to ask questions regarding the surgery, should any debriefing be required.

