### 5.1 Schedule of Evaluations

**Table 1. Schedule of trial events**

	Pre-op clinic visit	Day of procedure	First week post-op	Post-op visit
Agent Administration		X		
Informed consent	X			
Demographics	X			
Medical history	X			
Physical exam	X	X		X
Vital signs	X	X		X
Adverse event evaluation		X	X	X
Outcome evaluation (online survey)		X	X	X

For a day-by-day description, please refer to the prior section.

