### **5.5 Duration of Follow Up**

Patient are routinely called on post-operative day one to ensure a smooth recovery and answer any practical questions (dressings, wound care, etc.). Any unexpected outcomes will be recorded by the study nurse. Should a serious event occur, the patient will be forwarded to the emergency room for further evaluation.

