## 9. Measurement of Effect

### 9.1 Response Criteria

The patients will be prompted to complete online surveys administered through REDCap. REDCap allows for HIPAA compliant data gathering through this format. Surveys will include the following: a numerical rating scale (0 through 11) to rank current pain, number of narcotic tablets consumed since the prior survey, and overall satisfaction of pain control (binary yes/no).

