## 10. Data Reporting / Regulatory Considerations

### 10.1 Data Collection

The data collection plan for this study is to utilize REDCap to capture all treatment, toxicity, efficacy, and adverse event data for all enrolled patients. To ensure maximum compliance, subjects will be prompted with a text message to their mobile phone. To ensure HIPAA compliance, text messages will only read as "A new survey is due." Participants will be informed of this prompting protocol beforehand. No PHI, or any details of medical therapy, will be revealed in the text message or in the surveys administered through REDCap (please see the survey attachment to review how each survey will appear). Texts will be sent from a study dedicated phone controlled by the study staff. The study phone will be encrypted and managed by ITS per WCM regulation. Subjects will complete surveys at the following intervals: every 8 hours post-operative day 1 and 2, and every 12 hours post-operative day 3 through 7.

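### After the day-1 call, no dated or described method collects non-pain adverse events until the 2-3 week visit, although release is stated to last 72 hours

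*Combined protocol and SAP*

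**What the plan says.** - **Recording route (section 13).** "Adverse events will be recorded by the study nurse and clinical fellow during follow-up phone calls and clinic visits with each post-operative patient". The calls are plural and undated.
- **The one dated call (section 5.5).** "Patient are routinely called on post-operative day one to ensure a smooth recovery". The nurse is to record outcomes that were not expected. Section 5, under week 1, also describes a single standard-of-care call at which the nurse asks about complications and records them.
- **The next dated inquiry (section 5).** The clinic visit at 2-3 weeks.
- **Schedule (Table 1).** The row "Adverse event evaluation" is marked for the day of procedure, the first week and the post-op visit. The first-week mark has no day or method.
- **Surveys (sections 5, 9.1 and 10.1).** They are sent "every 8 hours post-operative day 1 and 2, and every 12 hours post-operative day 3 through 7". On content, section 5 says: "The surveys will ask the patients to rank their current pain (NRS-11), pain control satisfaction, and record the number of narcotic tablets required". Section 9.1 lists the same three items. Section 10.1 refers to the form itself: "please see the survey attachment to review how each survey will appear". That attachment is not among the documents available.
- **Exposure (section 2.2).** "the liposomal delivery vehicle provides an extended release over 72 hours". Standard bupivacaine is said to act for about 6 hours.
- **Use of the data (section 13).** Minor events are reviewed every 10 patients. An allergic, central nervous system or cardiac event triggers a temporary halt and review by the principal investigator.

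**The concern.** The study drug is distinguished from the control by how long it keeps releasing. Yet the only active inquiry with a date after discharge falls early in that release period, and the next comes two to three weeks later. In between, the men are contacted many times by survey, but the surveys as described do not ask about nausea, vomiting, urinary retention, wound problems, or allergic, neurological or cardiac symptoms.

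Two safeguards in section 13 depend on timely detection: the periodic review of minor events and the halt trigger for major ones. A short-lived symptom on day 2 or 3 would reach the log only if the patient volunteers it or remembers it at the visit. The sections also describe the inquiry differently: complications (section 5), unexpected outcomes (section 5.5) and all adverse events (section 12.1.3). Two nurses following the text could log different things.

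**Working it through.** The plan states no figure for this point, so the check is a comparison of the sections plus simple arithmetic.

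**1. Number of surveys.** Inputs are from section 10.1: every 8 hours for 2 days, then every 12 hours for 5 days.
2 × 24/8 + 5 × 24/12 = 6 + 10 = 16.
In the first 72 hours: 6 + 24/12 = 8. Table 1 also marks the online survey on the day of procedure and at the post-op visit, so the total may be slightly higher.

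**2. Share of the release period after the call.** Inputs are 72 hours of release (section 2.2) and a call on post-operative day 1 (section 5.5). The clock hour is not given, so it is an assumption and is varied.
Share = (72 − hour of call)/72.

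| Hour of call (assumed) | Hours left of 72 | Share |
|---|---|---|
| 12 | 60 | 83% |
| 18 | 54 | 75% |
| 24 | 48 | 67% |
| 36 | 36 | 50% |

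More than half of the release period follows the call if it is made before 36 hours.

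**3. Gap to the next dated inquiry.** With a call at 24 hours (day 1) and a visit at 2-3 weeks: 14 − 1 = 13 days to 21 − 1 = 20 days.

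**4. Effect on the review every 10 patients.** Section 11.2 plans 50 operations in 6 months: 50/26 weeks ≈ 1.9 per week. Operations in the last 2 weeks: 2 × 1.9 ≈ 4. In the last 3 weeks: 3 × 1.9 ≈ 6. If each review follows the tenth operation (an assumption), about 4 to 6 of those 10 men would not yet have had the visit. Their only dated post-discharge inquiry would be the day-1 call.

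**5. Is the survey treated as a safety source?** Section 13 lists pain scores, tablet tally and satisfaction as study-related data, separately from adverse-event data. Section 10.1 says REDCap captures adverse-event data, but section 12.1.3 shows that this is a log kept by research staff. No section names the patient survey as a source of adverse events.

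**The case against.** Several stronger readings are tempting, and the documents do not support them.

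- **That the day-1 call is the only safety contact, and the rest of the release period is unmonitored.** Section 13 speaks of calls in the plural, Table 1 schedules evaluation in the first week, and section 12 counts events that patients report. What can be said is that no further active inquiry is dated or described.
- **That the surveys ask nothing about adverse events.** Poor pain control is a listed minor event in section 13, and pain and satisfaction are surveyed every 8 to 12 hours. The gap concerns non-pain events and rests on the described content, because the form was not available. Section 9.4, which adds no further parameters, is about response and settles nothing on safety.
- **That half-lives measure the drug effect missed.** Section 2.2 gives half-lives but no link between concentration and effect. It also puts the peak level at 0.5-2 hours, on the day of procedure, when evaluation is scheduled.
- **That the safety comparison between arms would be biased.** No objective or analysis in sections 1 and 11 compares adverse events between arms. At the stated toxicity rate of about 1 in 50,000, 50 men would yield an expected 50/50,000 = 0.001 events, so such a comparison could not inform on major toxicity.

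It is also fair to say that the call in section 5 is an active inquiry, that infection, hematoma and dehiscence can be found at the wound check, and that dating further calls would be another remedy. All of this stands. It narrows the point to transient non-pain events after day 1 but does not remove it, since no section says how those are to be collected.

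**Conclusion.** The point holds in this limited form and should be acted on. Between discharge and the 2-3 week visit, the only dated active inquiry is the day-1 call. Table 1 and section 13 imply more but give no day or method, and the surveys as described have no item on non-pain events.

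For a call at 24 hours, 67% of the stated release period and 13-20 days without a dated inquiry follow. The share is 83% for a call at 12 hours and 50% for one at 36 hours. The practical loss is late or incomplete recording of transient events such as nausea, vomiting, urinary retention or neurological symptoms, which weakens the review every 10 patients and the halt trigger.

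The conclusion assumes that sections 5 and 5.5 describe the same call and that the survey form matches its description. If the attachment already carries safety items, what remains is to say so and reconcile the sections.

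**What to change.** - Add a short adverse-event checklist to the existing REDCap survey, once daily through day 7 and identical in both arms. Cover the categories already listed in sections 7.1 and 13.
- Have a positive answer alert the study nurse, who checks it and enters it in the adverse-event log.
- Name the survey as a source of adverse events in sections 5, 9.1 and 13.
- Reconcile the first-week mark in Table 1 and the undated calls in section 13 with the single call in sections 5 and 5.5. State when and how non-pain events are collected after day 1.
- Align what the nurse records under section 5.5 with the requirement in section 12.1.3 to record all adverse events.

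**Cost.** Slightly longer surveys, more minor events logged, some nurse time to check positive answers, a REDCap alert and an IRB amendment. Asking once a day rather than at every survey limits the burden. The sample size and the efficacy analysis do not change.
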